#### 6. Other Exclusion Criteria

- a) Prisoners or subjects who are involuntarily incarcerated
- b) Subjects who are compulsorily detained for treatment of either a psychiatric or physical (e.g., infectious disease) illness
- c) Non-compliance with or inability to complete eDiary during Observation Period. Non-compliance is more than 4 missed evening reports during the Observation Period.
- d) Exposure to non-biological investigational agents (other than rimegepant) within the 30 days prior to Screening visit.
- e) Exposure to biological investigational agents within the 90 days prior to Screening visit.
- f) Score of > 0 on the Sheehan Suicidality Tracking Scale (See Section 6.2.5) for the period of 30 days prior to screening.
- g) Previous enrollment in study BHV3000-201.
- h) Participation in any other investigational clinical trial while participating in this clinical trial.

Please see Section 5.4 for Prohibited medications and Section 5.5 for allowable migraine Medications

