4.4 Study Population

4.4.1 Subject Disposition

Subject disposition will be summarized for screened subjects by enrollment group and overall as the number and percentage of subjects in the following categories:

- Screened (identified as subjects with non-missing informed consent date and enrollment group)
- Did not enroll in the LTT period (identified as screened subjects with missing IWRS enrollment date)
 - Did not enter the OP (identified as a subset with missing OP start date)
 - Reasons for discontinuation, including not reported*
 - Entered the OP (identified as a subset with non-missing OP start date)
 - Reasons for discontinuation, including not reported*
- Enrolled in the LTT period (identified as screened subjects with non-missing IWRS enrollment date)
 - Not treated (identified as enrolled subjects with missing study drug dose start date)
 - Reasons for discontinuation, including not reported*
 - Treated (identified as enrolled subjects with non-missing study drug dose start date)
 - Ongoing (identified as treated subjects with missing study drug last dose date)
 - Completed* (identified as treated subjects with non-missing study drug last dose date who completed)
 - Discontinued* (identified as treated subjects with non-missing study drug last dose date who discontinued)
 - Reason for discontinuation, including not reported*

The categories marked in with “*” will be based on the Study Exit Status CRF.

Subject disposition will be also be summarized for treated subjects by all subgroups of interest defined in Section 4.2.6.

Participation in previous Studies BHV3000-301/302/303 will be summarized by enrollment group and overall for the following populations: screened; enrolled; treated. The number and percentage of subjects in each previous study (total; 301; 302; 303) and treatment group (rimegepant, placebo) will be presented for each population. Note that subjects may participate in multiple studies and be in both treatment groups.

A by-subject listing of subject disposition information, including the reason for discontinuation and previous study participation, will be presented based on the Study Exit Status CRF for screened subjects.

A by-subject listing of eligibility with inclusion and exclusion criteria will be provided for all screened subjects, not just those who have non-missing criteria.

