5 CONVENTIONS

5.1 General

5.1.1 *Output Layout*

A list of TLFs and corresponding templates will be presented separately in the Mock TLF document.

Refer to the BHV3000 Core SAP for TLF layout conventions.

5.1.2 *Duplicate Subjects*

If the same subject participates in the study more than once and is assigned more than one subject identifier, then the following conventions will apply to analyses:

- The subject identifier corresponding to the first treatment will be populated across all records in analysis datasets if the subject was treated. Otherwise, the subject identifier corresponding to the first enrollment will be populated if the subject was enrolled but never treated. Otherwise, the subject identifier corresponding to the first screening will be populated if the subject was never enrolled. This will ensure that the output shows unique subjects.
- Pre-treatment parameters (e.g., IWRS screening date, IWRS enrollment date, OP start/end dates, LTT start date, study drug first dose date, enrollment group, demographics, baseline characteristics, medical history, migraine history, cardiac and other risk factors, prior triptan response, current triptan response) will be derived using data only from the subject identifier identified in the previous bullet.
- On-treatment and follow-up parameters (e.g., LTT end date, study drug last/end dates, EOT visit date, last contact date) will be derived using data from all duplicate subject identifiers to ensure that protocol deviations, safety, exposure, migraine, and outcomes research endpoints will be assessed comprehensively.
- Subject disposition will be derived from study exit status data from the last duplicate subject identifier.

5.2 *Subgroups*

5.2.1 *Triptan Non-Responders*

Triptan non-responders are identified using the “Prior Triptan Response” Case Report Form (CRF) pages, which capture reasons for discontinuing triptans taken historically. The definition of triptan non-responder is based on the number of triptans that a subject failed for efficacy reasons. For each triptan and route of administration, the subject is asked the questions shown in [Table 4](#). A subject is considered to have failed a drug for efficacy reasons if they indicated “most or all of the time” for any of the reasons in the table.

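### SAP 5.1.2 takes a duplicate subject's disposition from the last identifier even if no drug was taken under it, so a treated subject who is later screened again is reported with the screening exit

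*SAP*

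**What the plan says.** SAP 5.1.2 (Duplicate Subjects) has four conventions for a person who holds more than one subject number.

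- **Which identifier is kept.** "The subject identifier corresponding to the first treatment will be populated across all records in analysis datasets if the subject was treated". If the person was never treated, the first enrollment is used, and failing that the first screening.
- **Pre-treatment data.** These come only from the identifier kept.
- **On-treatment and follow-up data.** These are "derived using data from all duplicate subject identifiers to ensure that protocol deviations, safety, exposure, migraine, and outcomes research endpoints will be assessed comprehensively".
- **Disposition.** "Subject disposition will be derived from study exit status data from the last duplicate subject identifier".

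SAP 4.4.1 (Subject Disposition) then builds the table. The treated row depends on dosing: "Treated (identified as enrolled subjects with non-missing study drug dose start date". The completed row is "Completed* (identified as treated subjects with non-missing study drug last dose date who completed", with a parallel row for discontinued subjects and their reasons. Categories marked with an asterisk "will be based on the Study Exit Status CRF". An asterisked line, "Reasons for discontinuation, including not reported", also appears under subjects who never enrolled in the long-term treatment period, so the same form supplies exit reasons for screening failures. The disposition table is repeated for treated subjects in every subgroup of interest.

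**The concern.** The first convention ranks identifiers by how far the person got: treated, then enrolled, then screened. The disposition convention uses order in time alone. The two agree unless the last identifier stopped at a lower level than an earlier one.

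That order of records is foreseeable. Protocol 7.2.1 assigns the subject number immediately after consent, before any study procedure, so a returning patient can hold a second number before eligibility is checked. Among the exclusions (Protocol 5.3, item 6g) is "Previous enrollment in study BHV3000-201", so a returning patient who is recognised after consent should fail screening under the new number. Enrollment also opened in stages. The 4-14 attacks group overlaps both earlier ranges, and SAP 2.1 describes a later re-opening of the 2-8 group.

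At stake is whether the disposition table for treated subjects reports how those subjects actually left treatment, and whether it agrees with the adverse-event tables.

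**Working it through.** The plan states no figure to reproduce here. The check applies the SAP 5.1.2 conventions and the SAP 4.4.1 categories to each possible order of two records.

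| Order of records | Counted as treated? | Exit under SAP 5.1.2 | Exit of the last treated identifier |
|---|---|---|---|
| Treated, stopped for AE; then screen failure | Yes | Screen failure | Discontinued for AE |
| Treated, completed; then screen failure | Yes | Screen failure | Completed |
| Screen failure; then treated, completed | Yes | Completed | Completed |
| Treated, stopped for AE; then treated again, completed | Yes | Completed | Completed |

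The subject is counted as treated in every row, because that status depends on the dose start date and the identifier of the first treatment is kept. The exit is wrong in the first two rows only.

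**Treated, then screen failure.** Completed, discontinued and reason all come from the exit form, and the form used is that of the untreated screening. A screening reason therefore appears beneath the treated subjects. A completer drops out of the completed row, and this SAP names no other source for completion status. A subject who stopped for an adverse event has that reason replaced.

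**Screen failure, then treated.** The last identifier is the treated one, so the exit is right.

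**Treated twice.** The exit comes from the second treatment. This agrees with the last dose date and end-of-treatment date, which are derived over all identifiers.

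**Adverse-event tables.** SAP 4.8.2 tabulates adverse events leading to study drug discontinuation for the on-treatment period and for all safety periods combined, and lists them by subject. SAP 5.1.2 pools safety data over all identifiers. In the first row of the table above, the event is therefore still counted there while the disposition table shows a different reason.

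**Size per affected subject.** Shift = 100 × 1/N percentage points, with N from the planned numbers in the protocol synopsis:

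- Overall: 100 × 1/2000 = 0.05
- 2-8 group: 100 × 1/1200 = 0.083
- 9-14 group: 100 × 1/600 = 0.167
- Every-other-day group: 100 × 1/200 = 0.5

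The number of affected subjects is not in the documents. For an assumed 1 to 10 overall, the range is 0.05 to 0.5 percentage points of 2000 (10/2000 = 0.5%).

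**The case against.** Disposition describes the end of participation, so taking the last record is a natural default, and departing from the ranking used for baseline data is not in itself an error. That is fair. The rule fails in one order of records only.

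That order also needs a narrow chain of events. The person must leave treatment, return, sign a new consent, receive a new number, and not be treated under it. A person recognised before consent gets no second number, and one never recognised and treated again is handled consistently. The documents report no actual case. This limits the likely count but does not supply the missing rule.

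The link to exclusion 6g has a version problem. SAP 1.1 says the SAP is based on Protocol Version 6, which added a cohort taking CGRP antagonist biologics. The protocol supplied has no such cohort and so appears to be an earlier version, and 6g cannot be confirmed for Version 6. The gap in SAP 5.1.2 does not depend on 6g, since any later untreated screening produces it.

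A reader might infer that the adverse-event discontinuation disappears from the report, or that the primary endpoint is biased. The documents do not support either. Safety data are pooled over all identifiers, and adverse events leading to discontinuation have their own tables and listing that do not draw on disposition. A reader might also infer that a subject treated twice has a first adverse-event exit wrongly overwritten. The later exit matches the pooled treatment dates, and the first event remains in the adverse-event tables.

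The Core SAP is not available and could hold further rules, but SAP 5.1.2 does not refer to it for the disposition of duplicates.

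**Conclusion.** The point holds in a narrow form. As written, SAP 5.1.2 gives the wrong completion status or reason for discontinuation to a treated subject whose last identifier was never treated, and no other text in this SAP corrects it. The error is confined to the descriptive disposition table and its subgroup versions, plus a visible disagreement with the adverse-event table when the true reason was an adverse event. No primary or secondary endpoint changes.

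The effect is 0.05 percentage points of 2000 per affected subject and 0.5 in the every-other-day group, assuming planned enrollment is reached. Any total depends on a count that the documents do not give, and no shift in a particular reason-for-discontinuation row can be calculated from them. This is a minor correction worth making because the rule is explicit and the repair is simple.

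**What to change.** Replace the disposition bullet in SAP 5.1.2 with:

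> Disposition is derived from the exit status of the last identifier under which the subject was treated; if never treated, the last identifier under which the subject was enrolled; otherwise the last screened identifier.

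This changes the result for treated subjects only when an untreated record follows treatment. Subjects who screen-failed and were then treated, and subjects treated twice, keep the exit they have now. The second clause applies the same logic to someone who enrolled, was never dosed, and was later only screened. No footnote is needed, because adverse-event discontinuations under any identifier are already tabulated and listed.

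The cost is one sentence in the SAP and a small change to the derivation program. No new data are required.

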5.2.2 CV Risk Contradicting Triptans

Subjects with CV risk that contraindicates triptans are identified using the “Cardiac and Other Risk Factors” CRF pages. The pages are used to identify subjects with CV conditions cited in triptan labels as contraindications. A subject is identified as someone with cardiovascular risk factors contraindicating triptans if any of the following questions are answered as “yes”:

- Does the subject have ischemic coronary artery disease?
- Does the subject have coronary artery vasospasm including Prinzmetal’s angina?
- Does the subject have Wolff-Parkinson-White Syndrome or arrhythmias associated with other cardiac accessory conduction pathway disorders?
- Does the subject have history of stroke or transient ischemic attack (TIA)?
- Does the subject have peripheral vascular disease (PWD)?
- Does the subject have ischemic bowel disease?
- Does the subject have uncontrolled hypertension?

5.2.3 Rimegepant Exposure

Rimegepant exposure subgroups are derived from parameters defined in Section 4.8.1 as follows:

- Time on rimegepant subgroups are based on quintiles of total weeks on treatment (< P20, ≥ P20 to < P40, ≥ P40 to < P60, ≥ P60 to < P80, ≥ P80) based on eDiary for treated subjects pooled across enrollment group. Percentiles will be rounded to 1 decimal place.
- Cumulative rimegepant exposure subgroups are based on quintiles of the total number of study drug tablets taken (< P20, ≥ P20 to < P40, ≥ P40 to < P60, ≥ P60 to < P80, ≥ P80) based on eDiary for treated subjects pooled across enrollment group. Percentiles will be rounded to integers.
- Average rimegepant exposure subgroups are based on average rimegepant exposure (tablets per 4 weeks), which is calculated as 4*cumulative rimegepant exposure/time in the LTT period for treated subjects pooled across enrollment group.

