4.6.3 Exploratory Safety and Other Endpoints

4.6.3.1 LFT Elevations

The number and percentage of subjects with LFT elevations will be summarized separately for the following populations and safety analysis periods:

- Screened subjects during pre-treatment by enrollment group, and overall
- Treated subjects during pre-treatment by enrollment group and overall
- Treated subjects on-treatment by enrollment group and overall
- Treated subjects on-treatment by subgroup level and overall for all subgroups of interest specified in Section 4.2.6
- Treated subjects on-treatment by enrollment group and overall for subjects who did not participate in previous Studies BHV3000-301/302/303
- Follow-up subjects during follow-up by enrollment group and overall.

LFT elevations include the following endpoints:

- Cumulative elevations:
 - ALT $> 1 \times, > 3 \times, > 5 \times, > 10 \times$, and $> 20 \times$ ULN
 - AST $> 1 \times, > 3 \times, > 5 \times, > 10 \times$, and $> 20 \times$ ULN
 - ALT or AST $> 1 \times, > 3 \times, > 5 \times, > 10 \times$, and $> 20 \times$ ULN
 - TBL $> 1 \times, 1.5 \times$, and $> 2 \times$ ULN
 - Alkaline phosphatase (ALP) $> 1 \times, > 1.5 \times$, and $> 2 \times$ ULN

- Mutually exclusive elevations:
 - ALT > ULN to $\leq 3 \times$ ULN, $> 3 \times$ ULN to $\leq 5 \times$ ULN, $> 5 \times$ ULN to $\leq 10 \times$ ULN, $> 10 \times$ ULN to $\leq 20 \times$ ULN, and $> 20 \times$ ULN
 - AST > ULN to $\leq 3 \times$ ULN, $> 3 \times$ ULN to $\leq 5 \times$ ULN, $> 5 \times$ ULN to $\leq 10 \times$ ULN, $> 10 \times$ ULN to $\leq 20 \times$ ULN, and $> 20 \times$ ULN
 - ALT or AST > ULN to $\leq 3 \times$ ULN, $> 3 \times$ ULN to $\leq 5 \times$ ULN, $> 5 \times$ ULN to $\leq 10 \times$ ULN, $> 10 \times$ ULN to $\leq 20 \times$ ULN, and $> 20 \times$ ULN
- Composite elevations:
 - ALT or AST $> 3 \times$ ULN and TBL $> 1.5 \times$ ULN
 - ALT or AST $> 3 \times$ ULN and TBL $> 2 \times$ ULN
 - ALT or ALT $> 3 \times$ ULN concurrent with TBL $> 2 \times$ ULN with Agresti-Coull 95% CIs (see Section 4.6.2)
 - ALT or ALT $> 3 \times$ ULN concurrent with TBL $> 2 \times$ ULN and ALP $\leq 2 \times$ ULN with Agresti-Coull 95% CIs (see Section 4.6.2)
 - ALT or AST $> 3 \times$ ULN concurrent with AEs of interest (nausea, vomiting, anorexia, abdominal pain, fatigue; see Section 4.6.3.2).

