Rates of multiple on-treatment, cumulative and mutually exclusive LFT elevations will be summarized using descriptive statistics for treated subjects (1) enrollment group and overall, and (2) subgroup level and overall for key extrinsic exposure factors. For each subject and LFT elevation endpoint, the rate is defined as total number of elevations/total number of non-missing values during the on-treatment period. Multiple values on the same collection date will be counted only once.

The number and percentage of subjects with time to first on-treatment LFT elevations ($ALT > 3 \times ULN$; $AST > 3 \times ULN$; ALT or $AST > 3 \times ULN$) will be presented by enrollment group and overall for treated subjects with on-treatment LFT elevations in the following categories: ≤ 2 , > 2 to ≤ 4 , > 4 to ≤ 8 , ..., > 48 to ≤ 52 , > 52 weeks. Time to elevation is calculated as $(LFT \text{ collection date} - \text{study drug first dose} + 1)/7$.

In all of these analyses described in this section, subjects must have non-missing LFT data (i.e., ALT , AST , TBL , or ALP) in the safety analysis period to be included.

4.6.3.2 *ALT or AST > 3 x Upper Limit of Normal (ULN) Concurrent with Nausea, Vomiting, Anorexia, Abdominal Pain or Fatigue*

AST or $ALT > 3 \times ULN$ elevations that are concurrent with nausea, vomiting, anorexia, abdominal pain or fatigue will be summarized, as the number and percentage of subjects experiencing this concurrently, in the same table as other LFT elevation endpoints described in Section 4.6.3.1. For a given safety analysis period (pre-treatment, on-treatment, follow-up), an LFT elevation is concurrent with an AE of interest if the imputed AE start date is $+\/- 7$ days inclusive of the LFT collection date; both the LFT collection date and the imputed AE start date must also be in the safety analysis period. Refer to the BHV3000 Core SAP for AE start date imputation. The following will be used to identify the AEs of interest: nausea, vomiting, anorexia, fatigue, and those containing “abdominal pain”.

4.6.3.3 *LFT Elevations by Gender, Age, and Rimegepant Exposure*

See Section 4.6.3.1.

4.6.3.4 *Secondary Safety Endpoints by Rimegepant Exposure*

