Secondary safety endpoints as described in Section 4.6.2 will be assessed by several study drug exposure groups for treated subjects. The number and percentage of subjects with hepatic-related SAEs by SOC, PT and severity, hepatic-related AEs leading to study drug discontinuation by SOC and PT, and concurrent elevations of AST or $ALT > 3 \times ULN$ with $TBL > 2 \times ULN$ will be shown by subgroup level and overall for extrinsic exposure subgroups (see Section 4.6.2). Only treatment-emergent AEs and on-treatment laboratory test values will be included.

4.6.3.5 *Number and Severity of Migraine Days per Month*

Subjects are instructed to report migraine status (yes, no, unable to recall) and severity (mild, moderate, severe, unable to recall) in their diaries every day.

Migraine days per month will be assessed as “migraine days per 4 weeks” to correspond with the 4-week visit schedule. Analyses will be based on the OP and LTT analysis periods for evaluable treated subjects, i.e., treated subjects who had ≥ 14 days of data (not necessarily consecutive) in both the OP analysis period and at least one 4-week interval in the LTT analysis period.

- A day of data is defined as an eDiary record with complete date and {yes or no} response to having a migraine. If a subject has multiple responses or migraine severities on the same date, then the most severe migraine last sequenced chosen. Only days of data are included in analyses.
- A migraine day is defined as a day of data with a “yes” response to having a migraine.
- 4-week (28-day) intervals are defined from LTT start as: interval 1 (≤ 4 weeks; LTT study days 1 to 28), interval 2 (> 4 to ≤ 8 weeks; LTT study days 29 to 56), ..., interval 13 (> 48 to ≤ 52 weeks; LTT study days to 336 to 364), interval 14 (> 52 to ≤ 56 weeks; LTT study days to 365 to 392). See Section 5.5 for the definition of LTT study days.

Thus, the total numbers of days of data and migraine days are calculated for the OP analysis period and for each 4-week interval in the LTT analysis period.

OP records will come from the screening epoch, whereas LTT records will be come from the treatment epoch.

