Drug accountability is provided by the site on the Drug Accountability CRF.

A by-subject listing will present eDiary exposure (i.e., number of tablets taken) and drug accountability for treated subjects.

Another by-subject listing will present eDiary exposure (i.e., total number of tablets taken) in 4-week intervals during the LTT for treated subjects. This will also display cumulative rimegepant exposure from both sources (i.e., eDiary and drug accountability), and flag subjects with ≥ 10 cumulative tablet difference between the 2 sources.

Another by-subject listing will present batch numbers for treated subjects.

eDiary Exposure

eDiary exposure will be summarized descriptively for treated subjects by enrollment group and overall, and will include the following parameters:

- Time in the OP (weeks), defined as (OP end date – OP start date + 1)/7
- Time from enrollment to last contact (weeks), defined as (last contact date – IWRS enrollment date + 1)/7
- Time in the LTT period (weeks), derived as (LT_T end date – LT_T start date + 1)/7
- Time on rimegepant (weeks), derived as (study drug end dose date – study drug first dose date + 1)/7.*
- Cumulative rimegepant exposure (tablets), derived by summing number of tablets across records with complete dates for subjects who reported taking study medication during the treatment epoch in the eDiary.*
- Average rimegepant exposure (tablets per 4 weeks), derived as 4*cumulative rimegepant exposure/time in the LTT period.*
- Number and percentage of subjects in the average rimegepant exposure (tablets per 4 weeks) categories defined in Section 4.2.6, and also in the following categories:
 - ≥ 12.6 ($\geq 90\%$ compliant with EOD dosing)
 - ≥ 11.2 ($\geq 80\%$ compliant with EOD dosing)
- Number and percentage of subjects who took more than 1 tablet per day on any day. This could be from the same bottle or different bottles due to an unscheduled visit.
- Exposure over time, as defined by the number and percentage of subjects who took
 - ≥ 8 tablets per 4 weeks for 4, 8, 12, 16, 20, ≥ 24 , ≥ 12 , and ≥ 4 weeks. These categories correspond respectively to 1, 2, 3, 4, 5, ≥ 6 , and ≥ 3 4-week intervals that are not necessarily consecutive (see below)
 - ≥ 12 tablets per 4 weeks for 4, 8, 12, 16, 20, ≥ 24 , ≥ 12 , and ≥ 4 weeks
 - ≥ 13 tablets per 4 weeks for 4, 8, 12, 16, 20, ≥ 24 , ≥ 12 , and ≥ 4 weeks

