 - ≥ 14 tablets per 4 weeks for 4, 8, 12, 16, 20, ≥ 24 , ≥ 12 , and ≥ 4 weeks (the “ ≥ 12 weeks” category will support the subgroup “treated subjects who took ≥ 14 tablets per 4 weeks for ≥ 12 weeks” specified in Section 4.2.6)
 - ≥ 20 tablets per 4 weeks for 4, 8, 12, 16, 20, ≥ 24 , ≥ 12 , and ≥ 4 weeks
 - ≥ 25 tablets per 4 weeks for 4, 8, 12, 16, 20, ≥ 24 , ≥ 12 , and ≥ 4 weeks
- Total rimegepant exposure (tablets) summed across all subjects, derived by summing cumulative exposure across all subjects
- Total rimegepant exposure (patient-years), derived by summing (study drug end dose date – study drug first dose date + 1)/365.25 across all subjects.

This summary will also display quintiles (e.g., P20, P40, P60, P80, where “PX” denotes Xth percentile) for asterisked (“*”) continuous parameters to support the derivation of rimegepant exposure subgroups (see below). See Section 5.3 for derived dates.

eDiary exposure over time will assess the number of 4-week (28-day) intervals in which a subject exceeded select tablet counts in the LTT analysis period (see Section 5.4), where the number of 4-week intervals are not necessarily consecutive. For example, suppose a subject takes 20 tablets through 4 weeks (interval 1; LTT study days 1 to 28), 10 tablets after 4 weeks to 8 weeks (interval 2; LTT study days 29 to 56), 25 tablets after 8 weeks to 12 weeks (interval 3; LTT study days 57 to 84), and 15 tablets after 12 weeks to 16 weeks (interval 4; LTT study days 85 to 112). Thus, this subject is considered to have taken ≥ 14 tablets per 4 weeks for 12 weeks (i.e., intervals 1, 3 and 4), ≥ 20 tablets per 4 weeks for 8 weeks (i.e., intervals 1 and 3), and ≥ 25 tablets per 4 weeks for 4 weeks (i.e., interval 3). See Section 5.5 for the definition of LTT study days.

eDiary exposure will also be summarized by subgroup level and overall for treated subjects for all subgroups of interest described in Section 4.2.6.

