- TEAEs occurring in $\geq 2\%$ of subjects in any enrollment group after rounding. Percentages will be displayed rounded to integers, and AEs will be displayed in alphabetical order by SOC and PT.
- AEs occurring in $\geq 2\%$ of subjects in any enrollment group or subgroup level[^]
- AEs occurring in $\geq 5\%$ of subjects in any enrollment group by severity (primary safety endpoint, see Section 4.6.1)
- AEs occurring in $\geq 10\%$ of subjects in any enrollment group
- Exposure-adjusted AEs
- AEs related to study drug by severity*
- AEs related to study drug occurring in $\geq 2\%$ of subjects in any enrollment group or subgroup level[^]
- SAEs (primary safety endpoint, see Section 4.6.1)*
- Exposure-adjusted SAEs
- AEs leading to study drug discontinuation (primary safety endpoint, see Section 4.6.1)*
- Hepatic-related AEs by severity (secondary safety endpoint, see Section 4.6.2)[#]
- Hepatic-related SAEs[#]
- Hepatic-related AEs leading to study drug discontinuation (secondary safety endpoint, see Section 4.6.2)[#]
- Additional AEs of special interest: potential drug abuse[^]; CV; suicidality. Potential drug abuse AEs will be displayed in alphabetical order by severity and PT without SOC.

Endpoints marked with “*” will also be summarized by subgroup level and overall for all subgroups of interest specified in Section 4.2.6. Endpoints marked with “#” will also be summarized by subgroup level and overall only for extrinsic exposure factors (see Section 4.2.6). Endpoints marked with “^” will also be summarized by subgroup level and overall only for key extrinsic exposure factors (see Section 4.2.6).

Refer to the BHV3000 Core SAP for exposure-adjusted AEs. Calculations for on-treatment exposure-adjusted AEs will set reference start date to the study drug first dose date, reference end date to the study drug end dose date, and reference last date to the study drug last dose date + 7 days.

Follow-up AEs

Follow-up AEs will be summarized by SOC and PT for follow-up subjects by enrollment group and overall for the following endpoints:

- AEs by severity
- SAEs.

AEs in All Safety Analysis Periods Combined

AEs in all safety analysis periods combined (i.e., pre-treatment, on-treatment, and follow-up) will be summarized by SOC and PT for treated subjects by enrollment group and overall for the following endpoints:

- AEs leading to study drug discontinuation (primary safety endpoint, see Section 4.6.1)

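### Crude percentages of liver events by quintile of final weeks and tablets do not show risk by exposure: with constant risk they can fall, rise or look mixed.

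*SAP*

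**What the plan says.** One exploratory objective (SAP 1.2.3) is to find the time on treatment and cumulative exposure that go with hepatic SAEs, hepatic discontinuations, and ALT/AST elevations above 3x ULN concurrent with bilirubin above 2x ULN. The matching estimand in SAP Table 3 is a frequency by exposure subgroup.

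SAP 5.2.3 defines the subgroups from final totals, pooled over enrollment groups:
- "Time on rimegepant subgroups are based on quintiles of total weeks on treatment"
- "Cumulative rimegepant exposure subgroups are based on quintiles of the total number of study drug tablets taken"

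SAP 4.8.1 gives the time variable: "Time on rimegepant (weeks), derived as (study drug end dose date – study drug first dose date + 1)/7".

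Three sections place numbers and percentages of patients in these subgroups:
- SAP 4.6.3.1, LFT elevations: "Treated subjects on-treatment by subgroup level and overall for all subgroups of interest specified in Section 4.2.6".
- SAP 4.6.3.4, hepatic SAEs, hepatic discontinuations and concurrent elevations: "will be shown by subgroup level and overall for extrinsic exposure subgroups".
- SAP 4.8.2, hepatic AE tables: "will also be summarized by subgroup level and overall only for extrinsic exposure factors".

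SAP 4.2.4 plans no covariate adjustment or stratification.

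**The concern.** Final weeks and final tablets are settled only when treatment ends, and a liver event can be what ends it. Two mechanisms act in opposite directions even if exposure has no effect.

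- **The event stops treatment.** The patient's totals are cut short and the event lands in a low quintile. This is true by definition for hepatic AEs leading to discontinuation.
- **The event does not stop treatment.** Patients in high quintiles have been observed for longer and had more liver tests, so more of them have an event.

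Protocol 6.5 and 8.1.5 leave discontinuation after a liver finding to case-by-case judgment. For the other endpoints the mix of the two mechanisms, and so the direction of the pattern, cannot be known in advance.

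Protocol 1.3.4 names liver test changes as the main adverse event to watch. A falling pattern could be read as reassurance about long use, and a rising one as a cumulative-dose signal, when neither exists.

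**Working it through.** The plan gives no figure for the quintile tables, so there is none to reproduce. Its only numerical justification, the zero-event bounds in SAP 4.1, is correct (3/2000 = 0.0015; 3/800 = 0.00375) and does not bear on this point.

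**Step 1. Testing opportunity, from the documents.** Protocol Tables 1 and 2 schedule liver tests at Weeks 2, 4, 8 and every 4 weeks to Week 52 (14 draws), or at Weeks 2, 4, 8 and 12 (4 draws). With equal per-draw risk p, the ratio of the chances of any elevation is [1 − (1 − p)^14] / [1 − (1 − p)^4]. This is 3.48 at p = 0.001 and 3.41 at p = 0.005 (p assumed). Fourteen is a maximum: the on-treatment period closes 7 days after the last tablet (SAP 5.4), so a Week 52 draw may fall outside it.

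**Step 2. Time at risk.** At an assumed constant hazard of 2% per year, the chance of an event is 1 − exp(−0.02 × 364/365.25) = 1.97% over 52 weeks and 1 − exp(−0.02 × 84/365.25) = 0.46% over 12 weeks, with no exposure effect. If every event stops treatment, a completer has by construction had almost no chance to be a case.

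**Step 3. Simulation with no exposure effect.** From the documents: 1200/600/200 patients, treatment for 52/52/12 weeks, time on drug from first to last tablet, and SAP 5.2.3 rounding of the cut points. Assumed: hazard 2% per year in every group; 40% exponential dropout over 52 weeks; tablets at 2-8 or 9-14 per 4 weeks, or alternate days plus 0-4 extra; 0, 50 or 100% of events stop treatment. Percentage with an event:

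| Subgroup | Events stopping treatment | Q1 | Q2 | Q3 | Q4 | Q5 |
|---|---|---|---|---|---|---|
| Tablets | none | 0.6 | 1.3 | 1.4 | 1.9 | 1.9 |
| Tablets | half | 2.0 | 1.4 | 1.2 | 1.4 | 1.2 |
| Tablets | all | 3.3 | 1.3 | 1.1 | 1.0 | 0.5 |
| Weeks | none | 0.3 | 1.0 | 1.9 | 1.9 | 2.0 |
| Weeks | all | 2.6 | 3.2 | 1.2 | 0.08 | 0.02 |

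Letting treatment end anywhere within ±7 days of schedule changes no entry by more than 0.2 percentage points.

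**Step 4. Other inputs.** A separately coded simulation used 52-week risks of 1, 3 and 10%, dropout of 20, 40 and 60%, lower tablet use (about 4, 8 and at least 14 per 4 weeks) and the 7-day tail.
- All events stop treatment: Q1 exceeds Q5 in every scenario, about 31- to 108-fold for weeks and 3- to 7-fold for tablets.
- No event stops treatment: Q5 exceeds Q1 in every scenario, about 4- to 10-fold for weeks and 1.6- to 5-fold for tablets.
- Half stop: mixed. At 3% risk and 40% dropout, the week quintiles read 1.8, 3.6, 2.4, 1.5, 1.6%.

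**Step 5. Would patient-years per quintile repair it?** SAP 4.8.1 provides them: "eDiary exposure will also be summarized by subgroup level and overall for treated subjects for all subgroups of interest described in Section 4.2.6". In the 2% model, events per 100 patient-years within final tablet quintiles are 1.8 to 2.1 if no event stops treatment (true value 2.0), but fall from 10.7 to 0.5 if all do. The repair works only for events that do not stop treatment.

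**Step 6. Time-updated bands.** Splitting both events and person-time by time since first dose (0-4, >4-12, >12-24, >24 weeks) or by tablets to date (0-20, >20-50, >50-100, >100) gives 1.8 to 2.3 per 100 patient-years in every 2% scenario. In the second simulation (3% risk, 40% dropout, true value 3.06), the bands by time since first dose give 3.01 to 3.12 when events stop treatment and 2.87 to 3.14 when they do not.

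**The case against.** The SAP plans several outputs that bear on the same question:
- time to first ALT/AST elevation in bands from first dose, elevations per measurement, eDISH and by-subject plots over time, and exposure-adjusted LFT rates (4.6.3.1);
- average tablets per 4 weeks as a subgroup, which measures intensity rather than a total (4.2.6);
- Kaplan-Meier time to discontinuation and tablets per 4-week interval for each patient (4.8.1);
- exposure-adjusted AEs and SAEs, and a listing of hepatic AEs (4.8.2).

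The SAP also calls its summary a frequency, not a risk. For hepatic discontinuations the numerators do show exposure at the event. The tables are exploratory, events may be few, and the Core SAP and Mock TLF document might add more. On this view a footnote and a case listing would be enough.

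Much of this is fair, but gaps remain in the SAP text. Time to first elevation covers ALT and AST only and is tabulated "for treated subjects with on-treatment LFT elevations in the following categories", so it has no at-risk denominator. Elevations per measurement are planned by the key factors, not by the quintiles. The exposure-adjusted LFT table covers the cumulative thresholds, whereas the concurrent bilirubin pairing is listed under composites. The exposure-adjusted AE and SAE tables are not marked for exposure subgroups and carry hepatic terms one by one. No output described gives a rate by tablets to date, or a tabulated rate over time for hepatic AEs, hepatic discontinuations or concurrent elevations. The plots and listings show individual cases but give no rate.

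Sparsity is a real limit: at 0.5% per year about 8 events occur per trial, or 0.6 to 3.4 per band.

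**Conclusion.** The concern holds. As specified, the quintile percentages cannot be read as risk by exposure: one constant risk gives 0.6% to 1.9%, 3.3% to 0.5%, or a mixed pattern across tablet quintiles, depending only on how often the event ends treatment.

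The sizes rest on assumed hazard, dropout, tablet use and stopping share. The end-to-end direction did not change within the ranges tried when all events or none stopped treatment. The pattern need not be monotone: the week quintiles peak in the second group when all events stop treatment, and level off among 52-week completers when none do. The roughly 20 patients treated for 12 weeks alongside a CGRP biologic (SAP 2.1) were not modelled separately.

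The consequence is limited to exploratory, descriptive tables. No test and no primary or secondary frequency changes. The correction is still worth making, because these tables are the named answer to a stated liver-safety objective. Core SAP and Mock TLF content was not available to check.

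**What to change.** 1. For LFT and hepatic endpoints, including concurrent bilirubin elevations, add events per patient-year by time since first dose (for example 0-4, >4-12, >12-24, >24 weeks) and by cumulative tablets to date. Split both events and person-time by band and end person-time at the first event. Show results overall, and by enrollment group only where counts allow.
2. Add hepatic AEs as a group, and hepatic AEs leading to discontinuation, to the exposure-adjusted tables.
3. List weeks and tablets to date at onset for each hepatic case, unless the Core SAP listing already does so. With few events this will be the most useful output.
4. If the quintile tables stay, footnote that total exposure depends on the outcome and on the 12- or 52-week schedule, so the percentages are not risk by exposure.

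The cost is SAP wording and programming, with some sparse cells. Daily eDiary tablets, LFT dates, AE dates and 4-week intervals are already collected or derived.
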